The **evaluation** of BPD includes a blood gas, a chest x-ray, and an assessment of the patient's nutritional status. Arterial blood gas may reveal hypoxia, hypercarbia, or acidosis. These patients remain on continuous pulse oximetry to achieve adequate oxygen saturation.

Chest radiographs may show decreased lung volumes, hyperinflation, areas of atelectasis, pulmonary oedema, and pulmonary interstitial emphysema. High-resolution CT (computed tomography) may show abnormalities not readily seen on routine chest radiographs. Infants with moderate or severe BPD should be screened for pulmonary hypertension (PH) by echocardiography (ECHO) at 36 weeks postmenstrual age (PMA).

The **diagnosis** of BPD is made clinically based on gestational age (GA), postmenstrual age, oxygen exposure and oxygen requirements at 36 weeks PMA. In 2001, the National Institute of Child Health and Human Development (NICHD) workshop proposed the current definition, in which infants born at less than or equal to 32 weeks GA with 28 days of oxygen exposure are diagnosed with mild, moderate, or severe BPD at 36 weeks PMA based on their respiratory support at that time.

The global aim in the **management** of infants with BPD is to support them during lung growth occurs, limit further lung injury, optimise lung function and detect complications associated with BPD.(34) Some measures include:

- Nutrition: they require an increased amount of energy, their nutritional requirements can be up to 140-150 Kcal/kg/day
- Fluid restriction: restriction to a total fluid volume of 120-150 ml/kg/day
- Minimise ventilator-associated lung injury: non-invasive ventilation is preferred if possible. If invasive ventilation is required, early extubation is recommended.

- The target saturation should be between 90 and 94%.
- Pharmacological interventions: possible use of systemic corticosteroids, diuretics, or bronchodilators

Sepsis

Neonatal sepsis is a systemic condition caused by bacteria, viruses, or fungi that results in haemodynamic changes and clinical symptoms, leading to significant morbidity and mortality.

When discussing sepsis in neonates, it is important to distinguish between two different types of sepsis, which have different epidemiology, aetiology, risk factors, and management.

Early-onset sepsis (vertical sepsis)

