3.2.8 Treatment

The aim of modern RDS management is to **maximize survival** while **minimizing complications**.

Oxygen supplementation over stabilization

In preterm babies receiving oxygen, the **target saturation should be between 90% and 94%**, so the alarm thresholds should be set at 89% and 95%.

Due to the high risk of having retinopathy of prematurity (ROP) in preterm infants, it is important to have protocols for screening and treating preterm babies for ROP.(47)

Surfactant administration

Surfactant is not administered to all newborns with RDS. If it is administered, it should be given early in the course of the disease. These are the **criteria recommended for surfactant administration** by the European Consensus Guidelines on the Management of Respiratory Distress Syndrome (47):

- Preterm babies < 30 weeks of gestation requiring intubation for stabilization.
- Worsening babies with RDS if $FiO_2 > 0.30$ on CPAP pressure ≥ 6 cm H₂O or if lung ultrasound suggests surfactant requirement.
- A second and occasionally a third dose of surfactant should be given if there is persistent evidence of RDS, such as persistent high oxygen requirements and other problems have been excluded.

It is recommended the use of natural surfactant given by LISA technique (less invasive surfactant administration) when the baby is on CPAP. The LISA technique uses a thin catheter for surfactant administration, and completely avoids “bagging”, allowing the infant to maintain spontaneous breathing on CPAP while surfactant is gradually delivered in small aliquots.

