4. JUSTIFICATION

Neonatal respiratory distress syndrome is the most common complication of prematurity. Its incidence increases with the lower gestational age, so that the babies most affected are those born at less than 32 weeks' gestation (40,61). In general, these are the babies with the greatest complications of prematurity, so it is important to try to reduce their morbidity and mortality.

Up to 40%(61) of these premature babies with NRDS require invasive mechanical ventilation to manage the syndrome. According to some studies and the European NRDS guidelines (47), it is recommended that babies are intubated for as short a time as possible.

Weaning, the step before extubation, is **essential for safe extubation**. Although there are two main weaning protocols, there are **no studies** to show which one is better for these neonates.

Demonstrating which of the two weaning protocols currently used is more effective is essential to reduce the morbidity and mortality associated with this syndrome.

The aim of this research is to determine which of the two protocols results in fewer reintubations and shorter weaning times. Studies suggest that a lower number of these variables may lead to a lower incidence of complications associated with NRDS, thereby reducing associated morbidity and mortality. If this research demonstrates that one protocol is superior, it could be implemented to make weaning more effective and reduce complications in premature babies with NRDS.

This study is also relevant because, although there are some studies on weaning in adults, there is practically no literature on these issues in the neonatal population. It is inappropriate to apply adult data to premature neonates due to the immature control of ventilation, the unique lung physiology, ventilation mechanics, and types of lung disease found in newborns.

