7.4 Variables and measurements

Independent variable

The independent variable is the **invasive mechanical ventilation protocol** used during the weaning. It is conceived as a **dichotomous qualitative nominal variable** and is expressed as PSV/ACVGV:

- PSV: Pressure support ventilation
- ACVGV: Assist control volume guarantee ventilation

Dependent variables

There are two dependent variables: **number of reintubations** and **time of weaning**.

The **number of reintubations** is the main dependent variable. It is a **discrete quantitative variable**. The higher the number of reintubations, the higher the risk of complications, so it is a good variable to determine which protocol is more effective. Extubation failure is defined as reintubation within 24-72 hours, so the number of reintubations will be counted for the first 72 hours after the extubation.

The **time of weaning** is the secondary dependent variable. It is a **continuous quantitative variable**. It is counted from the moment the weaning is started until the extubation is executed. The longer this time is, the greater the risk of complications arising from invasive ventilation that the child may have, so it is a good variable to determine which protocol is more effective.

Covariates

- **Gestational age at birth/type of preterm:** once is born, the baby will be classified into one of these categories. It is a *dichotomous qualitative ordinal variable*:
 - Extremely preterm (< 28 weeks of gestation)
 - Very preterm (28-32 weeks of gestation)
- **Birthweight:** it is a *continuous quantitative variable* measured in grams.
- **Sex:** it is a *dichotomous qualitative nominal variable*. Categorized as men or women.
- **CPR after birth:** it is a *dichotomous qualitative nominal variable*. It will be expressed as yes or no.

- **5-minute Apgar score** (see Annex 1): It is a quantitative variable, but categorized in the following intervals, resulting in a *polychotomous qualitative ordinal variable*:
 - Apgar 0-3
 - Apgar 4-6
 - Apgar 7-10
- **Risk factors of prematurity:**
 - **Previous preterm birth:** it is a *dichotomous qualitative nominal variable*. It will be expressed as yes or no.
 - **Second trimester miscarriage (> 16 weeks):** it is a *dichotomous qualitative nominal variable*. It will be expressed as yes or no.
 - **Multiple pregnancy:** it is a *dichotomous qualitative nominal variable*. It will be expressed as yes or no.

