7.5 Study intervention

In this study there will be two different protocols applied for weaning of invasive mechanical ventilation in extremely and very preterm newborns with NRDS: PSV and ACVGV. These protocols will be applied by professional neonatologists.

When an extremely or very preterm newborn is in invasive mechanical ventilation due to NRDS and meets all inclusion criteria and any exclusion criteria, an informative document (see Annex 4) and an informed consent (see Annex 5) will be given to the parents or legal guardians to sign.

Once the newborn enters the study, the neonatologists will wait until this patient meets the **criteria to start the weaning**. These criteria will be **precisely explained** in the document given to all hospital coordinators during the formation sessions. The weaning criteria are the following:

- Clinical criteria:
 - o Stable patient
 - o No intercurrent process that may hinder weaning

- Respirator parameters
 - o $FiO_2 < 40$ mmHg
 - o $PEEP < 7$ cmH₂O
 - o $RR < 50$ rpm
 - o $PIP < 20$ cmH₂O

When the patient meets the weaning criteria, the intervention will start. The intervention will be carried out by a neonatology expert. The patient will be randomly assigned in one of the two groups:

- o Group 1: The protocol used for the weaning will be **pressure support ventilation (PSV)**

- o Group 2: The protocol used for the weaning will be **assist control volume guarantee ventilation (ACVGV)**

Both protocols of weaning have been properly explained in section 3.3.3 *Invasive mechanical ventilation*.

The patient will remain in weaning until he or she meets the **criteria for extubation**. These criteria will be **precisely explained** in the document given to all hospital coordinators during the formation sessions. The patient will be extubated to a CPAP with a nasal PEEP of 6 mmHg. The extubation criteria are the following:

- Gasometrical criteria:
 - o pH > 7,3
 - o pCO₂ < 50 mmHg
 - o pO₂ > 70 mmHg
 - o Sat Hb 90-95% (haemoglobin saturation)

- Clinical criteria:
 - o Stable patient
 - o Without active infectious process
 - o Without hemodynamically significant ductus
 - o Neurologically capable of maintaining a patent airway

- Respirator parameters:
 - o PEEP < 6 mmHg
 - o FiO₂ < 30 cmH₂O
 - o RR < 20 rpm
 - o PIP < 20 cmH₂O
 - o Tidal volume 5 ml/kg

[figure not shown]

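### The extubation saturation criterion in section 7.5 is a closed 90-95% band with no room-air exception, so read literally it keeps a well-oxygenated infant intubated

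*Combined protocol and SAP*

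**What the plan says.** Section 7.5 makes the extubation list a gate: "The patient will remain in weaning until he or she meets the criteria for extubation". Under blood gases the list asks for pH above 7.3, pCO₂ below 50 mmHg, pO₂ above 70 mmHg and "Sat Hb 90-95% (haemoglobin saturation"). The oxygen setting is limited from above only, as "FiO₂ < 30 cmH₂O". I read this as 30%; the unit slip is a separate matter. No line mentions room air.

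The background sections use almost the same saturation range for another purpose. Section 3.2.8 says: "In preterm babies receiving oxygen, the target saturation should be between 90% and 94"%, and continues "so the alarm thresholds should be set at 89% and 95"%. The part of section 3.1.5 on bronchopulmonary dysplasia repeats the range: "The target saturation should be between 90 and 94"%. The reintubation list in section 7.5 treats saturation as a one-sided limit, below 90%.

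Section 7.4 defines weaning time, the secondary outcome: "It is counted from the moment the weaning is started until the extubation is executed".

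**The concern.** An upper limit on saturation makes sense when oxygen is being given: it tells staff to turn the oxygen down. It is not a test of whether an infant can breathe without the tube. Used as an extubation criterion without the supplemental-oxygen condition, it turns good oxygenation into a reason to withhold extubation.

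Two things are at stake. The first is avoidable time on the ventilator. The Justification (section 4) relies on guidance that points the other way: "it is recommended that babies are intubated for as short a time as possible". The second is the secondary endpoint, because the weaning clock runs to the extubation actually carried out. A delay caused by the ceiling would be counted as weaning time.

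**Working it through.** The plan gives no figure to reproduce here. The check is one of wording and logic.

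**Step 1. Shape of each oxygen-related line (sections 7.5 and 3.2.8).**

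| Item | Limit | Condition stated |
|---|---|---|
| Extubation, pH | above 7.3 | none |
| Extubation, pCO₂ | below 50 mmHg | none |
| Extubation, pO₂ | above 70 mmHg | none |
| Extubation, saturation | 90 to 95% | none |
| Extubation, FiO₂ | below 30 (read as %) | none |
| Reintubation, saturation | below 90% | none |
| Background oxygen target | 90 to 94%, alarms 89% and 95% | baby is receiving oxygen |

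Saturation is the only blood-gas line in the extubation list with a limit on both sides. The extubation band is one point wider at the top than the background target, so the two are close but not identical, and section 7.5 does not itself call its band a target. The difference that matters is the last column: the background target carries a condition that the extubation line lacks.

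**Step 2. Apply the list to an infant in room air.** Take FiO₂ 21%, saturation 97%, pO₂ above 70 mmHg, pH above 7.3, pCO₂ below 50 mmHg, and every clinical and ventilator line met.

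- FiO₂: 21 < 30, met.
- pH, pCO₂, pO₂: met by construction.
- Saturation: 97 > 95, not met.

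The infant fails on one line only. No added oxygen can be reduced to bring saturation down. Read literally, section 7.5 keeps this infant in weaning until saturation falls to 95% or below.

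**Step 3. Apply it to an infant on supplemental oxygen (FiO₂ above 21% and below 30%).** Saturation above 95% would already pass the upper alarm in section 3.2.8, so staff would lower the oxygen anyway. Here the ceiling adds little to the care the protocol already describes. The clear fault is confined to infants in room air, or to those who reach it while saturation is still above 95%.

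**Step 4. Apply a one-sided criterion.** With saturation of at least 90%, the infant in Step 2 passes (97 ≥ 90). The extubation limit (at least 90%) and the reintubation limit (below 90%) then meet without gap or overlap.

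**Step 5. Effect on the endpoints.** Weaning time ends at extubation, so any delay in Step 2 adds to it. The primary outcome, reintubations in the 72 hours after extubation, is counted from whenever extubation happens. Nothing in the text links the ceiling to that count.

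**The case against.** The strongest reply is that this is a fault of wording with little practical effect. A neonatologist would probably not leave an infant intubated for saturating at 97% in room air. Other lines may bind first: the same list requires a respiratory rate below 20, and section 3.3.3 says that under pressure support the patient starts every breath. Weaning time is recorded in days (Table 4 and Annex 7), so a brief reading above 95% would often leave it unchanged. Section 7.5 also says the criteria will be explained precisely in a document for hospital coordinators, which may deal with room air.

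Most of this stands, and it limits the size of the point. It does not make the line right: a bedside criterion that sensible staff must ignore should be rewritten. Section 10.3 says only that the coordinators' document will include the blood-gas criteria. It would be too strong to say that the document keeps the ceiling. All that can be said is that nothing visible removes it; the figure in section 7.5 and the flow chart in 7.6 cannot be seen either.

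A reader might also infer that the pO₂ floor of 70 mmHg and the 95% ceiling can hardly be met together. That depends on oxygen dissociation curves and blood-gas distributions that the documents do not give, so the point does not rest on it.

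**Conclusion.** The saturation line in the extubation list is wrong as written. It takes what is elsewhere an oxygen-titration range, drops the condition that the infant is receiving oxygen, and makes the upper end a bar to extubation. For an infant in room air above 95% who meets every other criterion, literal compliance means needless further ventilation and a longer recorded weaning time.

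The size is unknown: the documents give no distribution of saturation or FiO₂ at the end of weaning, and overrides would probably reduce the effect. The conclusion assumes that FiO₂ below 30 means 30%, that all listed criteria must hold together, and that the coordinators' document does not add an exception.

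A reader might infer that the ceiling biases the comparison of the two modes. The documents do not support that. The rule is the same in both arms, and although staff who know the allocation would decide any override, the text gives no sign that they would do so differently by arm. Nor is an effect on the primary endpoint shown.

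**What to change.** In section 7.5, and in the coordinators' document, write the extubation criterion as saturation of at least 90%. Keep 95% only as an oxygen-titration limit for infants on supplemental oxygen, in line with section 3.2.8.

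The cost is a wording change before recruitment, agreed with the five hospitals. It needs no extra patients, visits or procedures.

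Two further steps are optional and not part of correcting this error: a line on the Annex 7 form recording any extubation criterion that was overridden, and confirmation from the neonatology investigators that the pO₂ limit fits with the 90% floor.

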2. ABSTRACT

BACKGROUND:

The most common complication of prematurity is the newborn respiratory distress syndrome. It is a pathology that mainly affects premature infants born before 32 weeks of gestation. About 40% of these neonates require invasive mechanical ventilation to manage the syndrome. Recently, it has been recognised that reducing intubation time and the number of reintubations is of great significance in reducing further complications. Therefore, one approach to decrease complications is to identify a weaning protocol that facilitates posterior extubation.

OBJECTIVE:

The main objective is to compare the number of reintubations of *pressure support ventilation* and *assist control volume guarantee ventilation*, in extremely and very preterm neonates with newborn respiratory distress syndrome with invasive mechanical ventilation.

DESIGN:

This study is designed as a randomized, open label, multicentric clinical trial. It will be conducted in 5 different hospitals of Catalonia.

PARTICIPANTS:

542 participants will be enrolled from 5 hospitals using a stratified consecutive sampling, and the time of recruitment will be approximately of 2 years and two months. These patients will be randomized in two groups, one for each weaning protocol, with a 1:1 ratio.

KEYWORDS:

Neonates, preterm, newborn respiratory distress syndrome (NRDS), invasive mechanical ventilation, pressure support ventilation (PSV), assist-control volume guarantee ventilation (ACVGV), weaning, extubation

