Proposed Criteria for Failure During 2 Hours on CPAP < 5 cmH₂O or T-piece

Clinical Criteria:

- Diaphoresis
- Nasal flaring
- Increasing respiratory effort
- Tachycardia (increase in HR > 40 bpm)
- Cardiac arrhythmias
- Hypotension
- Apnea

Laboratory Criteria:

- Increase of PETCO₂ > 10 mmHg
- Decrease of arterial pH < 7.32
- Decline in arterial pH > 0.07
- PaO₂ < 60mmHg with an FiO₂ > 0.40 (P/F O₂ ratio < 150)
- SpO₂ declines > 5%

Table 3 - Criteria for extubation Readiness Test Failure (56)

Invasive mechanical ventilation in RDS

Despite best efforts to maintain as many preterm babies as possible on NIV, approximately **half of babies < 28 weeks will require invasive mechanical ventilation.** (57)

The aim of invasive mechanical ventilation is to achieve “acceptable” blood gases by ventilating at optimal lung volumes (while avoiding overdistension and atelectasis).

The initial tidal volume is usually set at around 5 ml/kg (58) with a maximum PIP of 25-30 cmH₂O. Adjustments to the initial tidal volume have to be done, according to assessment of work of breathing and blood gas evolution. Required tidal volumes vary around 5-7 ml/kg, the range tending to increase with increasing postnatal age.

PEEP should be adjusted to keep the lung open by finding a point where FiO₂ is at its lowest with haemodynamic stability and acceptable blood gases.

Once stabilised on invasive mechanical ventilation and with evidence of spontaneous respiratory effort, clinicians should immediately start planning for weaning to NIV. Some infants require a very short period of ventilation, particularly those with RDS following surfactant therapy, and early extubation of even the smallest babies who achieve low ventilator settings should be encouraged. (47)

Infant's size, absence of growth restriction, oxygen requirements and blood gases can all help to determine the success of extubation. (59) Delaying extubation does not improve the chances of success.

When weaning from invasive mechanical ventilation, it is reasonable to tolerate a modest degree of hypercarbia, provided the pH remains above 7.22.

Caffeine (20 mg/kg loading, 5-10 mg/kg maintenance) should be used to facilitate weaning from MV.(60)

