Once the extubation is done, the patient will be **followed up for 72 hours**. If during this follow up the patient meets the **reintubation criteria**, the newborn will be reintubated and this data will be properly collected. These criteria will be **precisely explained** in the document given to all hospital coordinators during the formation sessions. The reintubation criteria are the following:

- Gasometrical criteria:
 - o pH < 7,2
 - o pCO₂ > 60 mmHg
 - o pO₂ < 70 mmHg
 - o Sat Hb < 90% (hemoglobin saturation)

- Clinical criteria:
 - Progressive increase in work of breathing.
 - Frequent apnoeas requiring positive pressure ventilation.

- Respirator parameters in NIV:
 - PEEP > 6 mmHg
 - FiO₂ > 50 cmH₂O

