- 6. Formation sessions** (April 2024): An online meeting will be held with the whole team to provide theoretical training on neonatal resuscitation and neonatal mechanical ventilation. Particular emphasis will be placed on invasive mechanical ventilation and weaning. During this meeting, a consensual and detailed document will be sent to the hospital coordinators of each centre with the values of each parameter of the ventilator necessary for both the initiation of weaning and extubation. It will also include the clinical and gasometrical criteria for weaning, extubation and reintubation.

The aim of this training is to homogenise the process and reduce differences in the results between centres.

- 7. Creation of a database** (April 2024): A computer scientist will be hired to create a database, so that the data collected before, during and after the intervention can be correctly recorded.

STAGE 3: Sample recruitment, intervention, and data collection (27 months: May 2024 – July 2026)

8. Sample recruitment: As mentioned above, a consecutive stratified sampling method of extremely and very preterm newborns with NRDS that are on invasive mechanical ventilation, admitted to the NCIU of the participating hospitals will be carried out. Each co-investigator at each centre will be responsible for enrolling patients who meet all the inclusion criteria and any of the exclusion criteria, after the parents or legal guardians have signed the informed consent form (see Annex 5). Each participant will be randomised to one of the intervention groups of the clinical trial. The hospital coordinators of each centre will supervise this process.

Recruitment will continue until each centre has recruited the number of participants assigned by the stratification, with a 1:1 ratio. This is expected to take approximately 26 months (2 years and 2 months).

9. Intervention: During this period, patients will be assigned to one of the protocols for weaning, PSV in one arm of the study and ACVGV in the other.

This process can take a few days or even a few weeks, so an extra month has been added to the projected 26 months for this stage.

10. Follow up: After the intervention, all patients enrolled in the study will be followed for the first 72 hours after extubation, as all clinical data will be recorded in the baby's medical record.

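### Section 7.5 sets pO2 limits that do not fit its own saturation limits, at extubation and at reintubation, on usual oxygen dissociation curves

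*Combined protocol and SAP*

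**What the plan says.** **Extubation (section 7.5).** The gas criteria include pO2 above 70 mmHg and "Sat Hb 90-95% (haemoglobin saturation"), with pH above 7.3. The infant stays in weaning until the extubation criteria are met, and section 7.4 ends the weaning time at extubation.

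**Reintubation (section 7.5).** If the criteria are met within 72 hours, "the newborn will be reintubated and this data will be properly collected". There are three headed groups:
- Gas: pH below 7.2, pCO2 above 60 mmHg, pO2 below 70 mmHg, and "Sat Hb < 90% (hemoglobin saturation").
- Clinical: rising work of breathing, and frequent apnoeas needing positive pressure.
- Respirator: PEEP above 6, and FiO2 above 50 (printed with a pressure unit).

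No FiO2 is attached to the pO2 item, and no rule says whether one item, all items or one per group is needed. Further explanation is left to the coordinators' training document, of which section 10.3 says: "It will also include the clinical and gasometrical criteria for weaning, extubation and reintubation".

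**Elsewhere.** Section 3.1.5 says "The target saturation should be between 90 and 94"%, and section 3.2.8 repeats the range for preterm babies on oxygen: "target saturation should be between 90% and 94"%. Both are background; section 7.5 sets no saturation target after extubation. Table 3 in section 3.3.3, on failure of a pre-extubation readiness test, uses a conditional item: "PaO₂ < 60mmHg with an FiO₂ > 0.40". The Abstract states: "This study is designed as a randomized, open label, multicentric clinical trial". Annex 7 has one reintubation field and none for the criterion met.

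**The concern.** Oxygen tension and saturation are two measures of the same thing, tied together by the dissociation curve. Limits on both, in one list, should fall at roughly the same point of that curve. Here pO2 is cut at 70 mmHg while saturation is cut at 90%, or held within 90-95%, and on usual curves 70 mmHg lies well above 90%.

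Two outcomes are exposed. If the extubation pair is applied as printed, an infant kept within 90-95% may never show a pO2 above 70. Either extubation is delayed, which lengthens the secondary outcome and the time on the ventilator, or clinicians deviate. If the reintubation pO2 item can act alone, adequately saturated infants would be reintubated. That adds events to the primary outcome, and each is an avoidable procedure. The trial is open label and the treating team decides on reintubation.

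**Working it through.** The plan gives no figure of its own to reproduce here. The sample size of 271 per group does not enter the check.

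**Inputs from the plan.** pO2 limit 70 mmHg (both lists); saturation 90-95% (extubation) and below 90% (reintubation); background target 90-94%; FiO2 above 50; Table 3 limit of 60 mmHg with FiO2 above 0.40.

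**Assumption from outside the plan.** The documents give no dissociation curve and no haemoglobin mix. I used the Severinghaus curve, scaled by the half-saturation tension h (the pO2 at which haemoglobin is 50% saturated):

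S = 100 / (23400 / (x³ + 150x) + 1), with x = pO2 × 26.86 / h.

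I take h = 19-27 mmHg as the usual range, which allows for fetal haemoglobin, and carry the table to 32 to show where the conflict ends.

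**Worked line, h = 27, pO2 = 70.** x = 70 × 26.86 / 27 = 69.6; x³ + 150x ≈ 348,000; S = 100 / (23400 / 348,000 + 1) = 93.7%.

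| h (mmHg) | Saturation at pO2 70 | pO2 at 90% | pO2 at 94% | pO2 at 95% |
|---|---|---|---|---|
| 19 | 97.7% | 41.5 | 50.1 | 53.5 |
| 22 | 96.5% | 48.0 | 58.1 | 62.0 |
| 24 | 95.5% | 52.4 | 63.3 | 67.6 |
| 27 | 93.7% | 59.0 | 71.2 | 76.1 |
| 28 | 93.0% | 61.2 | 73.9 | 78.9 |
| 30 | 91.6% | 65.5 | 79.2 | 84.5 |
| 32 | 90.0% | 69.9 | 84.4 | 90.2 |

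A pO2 of 70 equals 95% at h ≈ 24.8, 94% at h ≈ 26.5 and 90% at h ≈ 32. A Hill curve with exponent 2.7 agrees broadly: at pO2 70 it gives 97.1% (h = 19), 93.0% (26.8) and 90.8% (30).

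**Extubation pair.** Both conditions hold only between the saturation at pO2 70 and 95%.
- h below about 24.8: no value satisfies both.
- h = 27: only 93.7-95%.
- h = 30: only 91.6-95%.
- h about 32: the full 90-95%.

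**Reintubation item.** pO2 below 70 is met across all of 90-94% at h below about 26.5, across 90-93.0% at h = 28, across 90-91.6% at h = 30, and nowhere in that range at about 32. Over h = 19-27 it is met 97.7 − 90 = 7.7 down to 93.7 − 90 = 3.7 saturation points above the list's own limit.

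**Consequence by combination rule.**
1. Any one item suffices: the pO2 item overrides the saturation limit, and infants at 90-94% would be reintubated.
2. All items required: saturation below 90% already implies pO2 below 70 for h up to about 32, so the pO2 item is redundant and causes no extra reintubation.
3. One item from each group required: reading FiO2 above 50 as 50%, and where that is the respirator item met, pO2 below 70 means a P/F ratio below 70 / 0.50 = 140. Table 3's item is 60 / 0.40 = 150. On this reading the limit is reasonable.

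**The case against.** The strongest reply is that harm at reintubation depends on a combination rule that the documents leave open. The same list has an FiO2 item, and if the groups are read together the pO2 limit is close to Table 3. If everything is required, the limit is merely superfluous. This stands: a reader might infer that the item is faulty under every rule, and the text does not show that.

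The second reply is that the curve is assumed, and that infants near reintubation may be acidotic, which shifts it to the right. This also stands in part. With a Bohr shift of 0.48 (assumed), adult haemoglobin gives an overlap of 90-91.6% at pH 7.30, about 90.0-90.3% at pH 7.25, and none at 7.20. Mainly fetal haemoglobin (h = 19.5 at pH 7.40) keeps the whole 90-94% range below 70 mmHg even at pH 7.20, where 94% corresponds to 64 mmHg. The argument has less force at extubation, because that list requires pH above 7.3. On adult haemoglobin h is then at most about 30, and the pair is still only partly attainable.

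The third reply is that the training document may settle it. That document could add a rule, but section 7.5 already prints the values it is to explain.

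A reader might also infer a loss of power or a biased comparison. A power figure would need the share of infants reintubated for pO2 alone, which appears nowhere in the documents. It would also depend on whether 16% is set against 26% or 6%. The same criteria apply in both arms, so the item by itself gives no reason to expect bias.

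**Conclusion.** The oxygenation limits in section 7.5 do not fit each other on usual curves. At h = 19-27 mmHg a pO2 of 70 corresponds to a saturation of about 94-98%; the conflict shrinks at 28-30 and vanishes at about 32.

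The extubation pair carries at least as much weight as the reintubation item, because its conditions read naturally as joint requirements and so need no assumption about a combination rule. The reintubation item is a problem if it can trigger reintubation alone, redundant if all items are needed, and reasonable if it must coincide with FiO2 above 50%.

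The conclusion rests on the printed limits and on the assumed curve. The number of infants affected is unknown.

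**What to change.** Before the training document is issued:

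1. **Extubation.** Remove the pO2 limit, or lower it to fit a saturation of 90-95%. On the curve above, 90% corresponds to about 42-59 mmHg at h = 19-27, so removal is simpler.
2. **Reintubation.** Replace the pO2 item with one tied to FiO2: for example Table 3's 60 mmHg with FiO2 above 0.40 (written there for a pre-extubation test), or saturation below 90% despite raised FiO2. The FiO2 condition is the essential part. A bare 60 mmHg would still cover all of 90-94% at h below about 22.7, and part of it up to about 27.
3. **Rule.** State that low pO2 alone does not trigger reintubation.
4. **Optional.** Add one Annex 7 field for the criterion met at each reintubation, so that the trial database records the reason.

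The cost is the rewording of two short lists and, if wanted, one form field. The downside is that the five centres must agree on the revised lists.
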